HAQ-DI	
A questionnaire validated for RA self-assessment by subjects that contains 20 questions in the following 8 functional areas:
 
 • Dressing and grooming • Arising

Term	Definition
	
 • Eating • Walking • Hygiene • Reach • Grip • Common daily activities 
Scoring within each functional area is from 0 (without any difficulty) to 3 (unable to do). The total score is obtained by summing 8 area scores and dividing by 8. The total HAQ-DI score ranges from 0 to 3 and corresponds to the current degree of disability:
 
 • 0 to < 1 Mild difficulties to moderate disability • 1 to < 2 Moderate disability • 2 to 3 Severe to very severe disability 
A HAQ-DI score reduction by 0.22 represents the MCID.

hsCRP	Marker of systemic inflammation associated with disease activity in RA that is generally not detectable with routine CRP assays.
ITT population	Primary analysis population comprising all enrolled and randomized subjects.
PTE population	Subjects from ITT population who received the assigned treatment through Week 12, have no major procedural protocol deviations, and for whom follow-up data are available.
RA disease activity assessments	
A standardized set of RA assessments that should be performed in the following order:
 
 • HAQ-DI • SGA • Subject's pain • TJC28 • SJC28 • EGA • hsCRP (mg/L)
RAMRIS	
A standardized method for MRI acquisition of the hand and wrist, joint pathology definitions and a scoring system for semiquantitative evaluation of:
 
 • Synovitis. 8 joints each scored on a scale from 0 (normal) to 3 (severe), resulting in a total score from 0 to 24 • Bone erosion. 25 bones each scored on a scale from 0 to 10, resulting in a total score from 0 to 250. Change by > 0.5 represents disease progression. • Osteitis. 25 bones each scored on a scale from 0 to 3, resulting in a total score from 0 to 75 • CARLOS (cartilage loss). 25 joints each scored on a scale from 0 to 4, resulting in a total score from 0 to 100
Randomization	Process of randomly assigning subjects to a treatment or control group which occurs after completion of Day 0 assessments.

Term	Definition

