If one of the components is missing at a given assessment point, no imputations will be done, and the CDAI value for that assessment will be set to missing. An imputation method for missing components may be applied as described in Section 5.8.1.

HAQ-DI score change from baseline

Change from baseline on the day of informed consent to Week 12 in mean HAQ-DI score as determined by subjects (see Section 8.2.5).

RAMRIS score and progression at Week 12

RAMRIS is the standardized system for RA MRI scoring of 4 different types of joint pathologies in the wrist and the hand. A total score for each pathology is generated by the summation of individual joint/bone scores as follows:

- *Synovitis*. 8 joints each scored on a scale from 0 = normal to 3 = severe, resulting in a total score from 0 to 24.
- *Bone erosion*. 25 bones each scored on a scale from 0 to 10, resulting in a total score from 0 to 250. An increase of > 0.5 from baseline to Week 12 will represent disease progression.
- *Osteitis*. 25 bones scored on a scale from 0 to 3, resulting in a total score from 0 to 75.
- *CARLOS (cartilage loss)*. 25 joints each scored on a scale from 0 to 4, resulting in a total score from 0 to 100.

Subjects will undergo MRI at Screening (baseline) and Week 12, and the MRI images will be scored by independent centralized blinded readers. Scores for each bone/joint will be calculated as the average of the score provided by each of the two readers. If a RAMRIS score from one of the readers is missing, then the RAMRIS score from the other reader will be used. If the score was

missing for both readers at any given time point, the average score is considered missing. An imputation method for missing components may be applied as described in Section 5.8.1. A listing will be provided that presents change in total score from baseline by subject for each of the RAMRIS pathologies. The number of observations and the total score change mean, minimum, maximum and 95% confidence interval will be presented for the treatment and control groups in a table.

The smallest detectable change (SDC) will be calculated for each of the joint pathologies to assess whether a patient experienced a change beyond measurement error. The SDC is calculated as:

$$\pm 1.96 \times \text{SD}_{\Delta(\text{CHANGE SCORES})} / (\sqrt{2} \times \sqrt{k})$$

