4.2 Exploratory Analysis

During the open-label follow-up, changes in exploratory efficacy endpoints at Week 24, 48, 96, 144 and 264 (end of study) will be evaluated in comparison to baseline and Day 0 for the treatment population and Week 12 for the crossover population using data for all subjects available at a given timepoint (**Table 2**). Refer to Section 5.2 for definitions of populations.

Table 2: Summary of Exploratory Efficacy Endpoints

Endpoint	Display	TOL	COL	Subgroup
ACR20/50/70 response	T, L	Y	Y	Y [1]
DAS28-CRP moderate/good EULAR response	T, L	Y	Y	Y
DAS28-CRP response (MCID)	T, L	Y	Y	Y
HAQ-DI score change and response (MCID)	T, L	Y	Y	Y
ACR components (TJC28, SJC28, Subject Pain, SGA, HAQ-DI, EGA, hsCRP) 20/50/70response	T, L	Y	Y	--
DAS28-CRP score change, LDA/remission	T, L	Y	Y	--
CDAI score change, LDA/remission, response (MCID)	T, L	Y	Y	--
RAMRIS (bone erosion, osteitis, synovitis, CARLOS) score change, progression (bone erosion) at Week 24	T, L	Y	Y	--
EQ-5D-5L score change	T, L	Y	Y	--
SF-36/PCS/MCS score change	T, L	Y	Y	--
Percent change in inflammatory biomarkers at Week 24	T, L	Y	Y	--
Subject satisfaction at Week 24	T, L	Y	Y	--

Abbreviations: ACR, American College of Rheumatology; CARLOS, cartilage loss score; CDAI, Clinical Disease Activity Index; COL, control to open label; CRP, C-reactive protein; DAS, Disease Activity Score; EGA, evaluator's global assessment; EQ-5d-5L, EuroQol 5 domains 5 levels; EULAR, European League Against Rheumatism; HAQ-DI, Health Assessment Questionnaire Disability Index; hsCRP, high sensitivity CRP; L, listings; LDA, low disease activity; RAMRIS, Rheumatoid Arthritis MRI Scoring System; SF-36, Short Form Survey with 36 items; SGA, subject's global assessment; T, tables; TJC, tender joint count; TOL, treatment to open label; SJC, swollen joint count; Y, yes.

[1] Subgroup analyses as defined in Section 6.3

Note: All score values are determined at all timepoints, unless stated otherwise. All response rates are determined based on change from baseline (i.e., on the day of informed consent for OL PTE population and Week 12 for CO PTE population) to a specified timepoint. Refer to Section 5.2 for definitions of populations Sections 6.2 for definition of response for specific endpoints.

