Progression rate from baseline (> 0.5)		
N [3]	xx (xx.x%)	xx (xx.x%)
Mean (SD)	xxx.x (xxx.xx)	xxx.x (xxx.xx)
Median	xxx.xx	xxx.xx
Min-Max	xxx.x – xxx.x	xxx.x – xxx.x
RAMRIS osteitis score		
Baseline [4]		
N [3]	xx (xx.x%)	xx (xx.x%)
Mean (SD)	xxx.x (xxx.xx)	xxx.x (xxx.xx)
Median	xxx.xx	xxx.xx
Min-Max	xxx.x – xxx.x	xxx.x – xxx.x
Week 24		
N [3]	xx (xx.x%)	xx (xx.x%)
Mean (SD)	xxx.x (xxx.xx)	xxx.x (xxx.xx)
Median	xxx.xx	xxx.xx
Min-Max	xxx.x – xxx.x	xxx.x – xxx.x
Change from baseline [4] (SDC: x.xx)		
N [3]	xx (xx.x%)	xx (xx.x%)
Mean (SD)	xxx.x (xxx.xx)	xxx.x (xxx.xx)
Median	xxx.xx	xxx.xx

Variable	TOL [1] (N=xxx)	COL [2] (N=xxx)
Min-Max	xxx.x – xxx.x	xxx.x – xxx.x
95% CI	(xx.x, xx.x)	(xx.x, xx.x)
RAMRIS CARLOS score		
Baseline [4]		
N [3]	xx (xx.x%)	xx (xx.x%)
Mean (SD)	xxx.x (xxx.xx)	xxx.x (xxx.xx)
Median	xxx.xx	xxx.xx
Min-Max	xxx.x – xxx.x	xxx.x – xxx.x
Week 24		
N [3]	xx (xx.x%)	xx (xx.x%)
Mean (SD)	xxx.x (xxx.xx)	xxx.x (xxx.xx)
Median	xxx.xx	xxx.xx
Min-Max	xxx.x – xxx.x	xxx.x – xxx.x
Change from baseline [4] (SDC: x.xx)		
N [3]	xx (xx.x%)	xx (xx.x%)
Mean (SD)	xxx.x (xxx.xx)	xxx.x (xxx.xx)
Median	xxx.xx	xxx.xx
Min-Max	xxx.x – xxx.x	xxx.x – xxx.x
95% CI	(xx.x, xx.x)	(xx.x, xx.x)

Abbreviations: CARLOS, cartilage loss score; CI, confidence interval; COL, Control to Open Label; RAMRIS, Rheumatoid Arthritis MRI Scoring System; SDC, Smallest Detectable Change; TOL, Treatment to Open Label

- [1] Treatment to Open Label (TOL): The TOL population comprises treatment subjects from ITT population who received active stimulation through Week 12, completed Week 12 assessments, continued to receive active stimulation during open-label follow-up, and for whom follow-up data are available.
- [2] Control to Open Label (COL): The COL population comprises control subjects from ITT population who received non-active (sham) stimulation through Week 12, switched to active stimulation after completing Week 12 assessments, continued to receive active stimulation during open-label follow-up, and for whom follow-up data are available.
- [3] Percentage calculated based on each analysis population (i.e., TOL, COL)
- [4] Baseline on the day of informed consent for TOL and Week 12 for COL
- [5] Initiation of stimulation at Day 0 for TOL and Week 12 for COL

Reference: Listing 16.x.x.x

SOURCE: xxxxx SAS 9.4 {program location} {run date/time} }

Table 14.8.2.14
 EQ-5D-5L

Variable	TOL [1] (N=xxx)	COL[2] (N=xxx)
EQ-5D-5L Index score		
Baseline [4]		
N [3]	xx (xx.x%)	xx (xx.x%)

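### RAMRIS change can mix one-reader and two-reader scores across visits, and erosion progression is fixed at > 0.5 without reference to the SAP's own smallest detectable change (minor; exploratory endpoints only)

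*SAP*

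**What the plan says.** CLP-004 (the interim and primary analysis SAP) section 8.6.1 sets the scoring rule: "Scores for each bone/joint will be calculated as the average of the score provided by each of the two readers". If one reader is absent, "If a RAMRIS score from one of the readers is missing, then the RAMRIS score from the other reader will be used". A score counts as missing only when it is "missing for both readers at any given time point, the average score is considered missing". CLP-008 (the long-term SAP) section 6.2.5 repeats these rules for Week 24.

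On progression, CLP-004 8.6.1 says: "An increase of > 0.5 from baseline to Week 12 will represent disease progression". Protocol section 3 has the same cut-off: "Change by > 0.5 represents disease progression". The CMH analysis list in CLP-004 8.6.2, Table 14.1.2.13 and Listing 16.1.2.6.8 all use this fixed value.

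The SDC is computed "to assess whether a patient experienced a change beyond measurement error". In the table shells it appears only as a label on the change-from-baseline row. No row counts subjects above it.

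For Week 24, CLP-008 Table 2 plans "RAMRIS (bone erosion, osteitis, synovitis, CARLOS) score change, progression (bone erosion) at Week 24". CLP-008 6.1 requires dichotomous variables to be shown as responders over patients, a percentage and a 95% CI.

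**The concern.** There are two routes by which reader disagreement can be read as erosion progression.

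The first is a change of reader set between visits. A two-reader mean at baseline compared with a single reader at Week 12 carries any systematic difference between the readers into the change score.

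The second is a cut-off not tied to measurement error. The SAP derives a patient-level error limit and then classifies patients by another number, which may be smaller.

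Erosion progression is the only yes/no structural endpoint in Protocol Table 3. False progressors in both arms would raise both rates and shrink a true difference.

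A separate matter is the Week 24 shell, Table 14.8.2.13. Its layout does not suit a yes/no endpoint, and it omits one of the four planned pathologies.

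**Working it through.** **Inputs.** From CLP-004 8.6.1: two-reader average, one-reader substitution judged per time point, cut-off > 0.5, and SDC = 1.96 × SD / (√2 × √k). Here SD is the standard deviation of the between-reader difference in change scores and k is the number of readers. The erosion scale reproduces: 25 bones × 10 = 250. The 0.5 cut-off has no derivation to reproduce. The SD and the missing-reader rate are not given, so the SD values below are assumptions.

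**Step 1: substitution at one visit, no true change.** Let readers A and B score at baseline and only B at Week 12.

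- Apparent change = B − (A + B)/2 = (B − A)/2.
- Example with A = 20 and B = 24: 24 − 22 = +2.0, a progressor. If B is lost instead: 20 − 22 = −2.0, which can hide progression.
- (B − A)/2 > 0.5 requires B − A > 1 point on the total.
- If the lower reader alone remains at baseline, the change is also inflated by half the gap.
- If the same reader is missing at both visits, the offset cancels: B − B = 0.
- Averaging is by bone or joint, so one missing bone carries over only half of that bone's gap.

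**Step 2: cut-off against SDC.** With k = 2, SDC = 1.96/2 × SD = 0.98 × SD. The cut-off is below the SDC when SD > 0.5/0.98 = 0.51. With k = 1, SDC = 1.96/√2 × SD = 1.386 × SD.

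**Step 3: chance of false progression, two readers at both visits.** Assume independent normal reader errors with variance s² at each visit and no true change. Each reader's change has variance 2s² and the difference between readers has variance 4s², so SD = 2s. The two-reader mean change has variance s², hence standard deviation SD/2. Then P(change > 0.5) = 1 − Φ(0.5 / (SD/2)).

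| Assumed SD | SDC (k = 2) | P(change > 0.5) |
|---|---|---|
| 0.5 | 0.49 | 2.3% |
| 1 | 0.98 | 15.9% |
| 2 | 1.96 | 30.9% |
| 4 | 3.92 | 40.1% |

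At the SDC itself the probability is 1 − Φ(0.98 × SD / (SD/2)) = 1 − Φ(1.96) = 2.5% for any SD.

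If bones are scored in whole numbers, which is not stated, two-reader averages move in steps of 0.5. A continuity correction at 0.75 then gives 1 − Φ(1.5), about 7%, at SD 1 and 1 − Φ(0.75), about 23%, at SD 2.

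**Step 4: single-reader changes.** Under the same assumptions, with no reader offset:

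- One reader at both visits: standard deviation √2 × s = 0.71 × SD.
- Mixed rule (two readers, then one): variance s² + s²/2 = 1.5s², standard deviation 0.61 × SD.
- Applying the k = 2 SDC to a single-reader change gives 1 − Φ(0.98/0.707), about 8%. The k = 1 SDC restores 2.5%.

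**Step 5: Week 24 shell.** In Table 14.8.2.13 the row "Progression rate from baseline (> 0.5" is followed by mean, SD, median and range. The Week 12 shell, Table 14.1.2.13, gives the same endpoint as a count and percentage. Table 14.8.2.13 has blocks for erosion, osteitis and CARLOS but none for synovitis, although CLP-008 Table 2 and 6.2.5 plan it.

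**The case against.** The strongest reply is that this is a small matter. RAMRIS is exploratory and outside the Hochberg family in CLP-004 8.5. Readers are central and blinded. Erosion is also analysed as mean score change by MMRM, so the structural result does not depend on the cut-off alone. All of that stands.

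The substitution bias needs most or all of a read to be lost at one visit but not the other. Protocol 12.4 provides for rejected images to be re-acquired within 7 days, and no missing-read rate is given. A reader might infer that reader differences are routinely counted as progression. The documents do not support that. They show only that the rule permits it.

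A reader might also infer that the progression rate is uninterpretable. That goes too far. The SDC is printed with the change score, the Week 12 listing shows each subject's change, and the > 0.5 definition is the protocol's own. If the SD is below about 0.51, the cut-off already exceeds the SDC and this part of the point disappears.

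It is equally tempting to conclude that Week 24 progression and synovitis would not be reported. CLP-008 6.1 already requires the right display for yes/no endpoints, and Listing 16.8.2.7.8 carries both a synovitis and a progression column. The fault is confined to the table shell.

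Finally, within-reader change has a price. It removes the offset but is noisier for single-reader subjects when the offset is small (0.71 against 0.61 × SD). What remains after these replies is that neither SAP says how single-reader scores enter a change, and that the SDC has a stated patient-level purpose but no patient-level output.

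**Conclusion.** The point holds as a minor one, for exploratory endpoints only. With no true change, a read lost at one visit adds or subtracts half the reader difference, so a gap above 1 point on the erosion total can create or mask progression. The fixed cut-off lies below the SAP's own SDC if the SD exceeds about 0.51. Under assumed SDs of 0.5, 1 and 2 the false-progression probability is about 2%, 16% and 31%, and lower if scores move in discrete steps. These figures rest on normal independent errors and on SDs that the documents do not supply.

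With blinded readers, misclassification should be similar in both arms. It inflates both rates and dilutes a difference. An inference that it favours one arm, or touches the primary or key secondary conclusions, has no support in the documents. The Week 24 shell error needs no assumption.

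**What to change.** 1. In CLP-004 8.6.1 and CLP-008 6.2.5, compute RAMRIS change within reader, using readers with scores at both visits, then average over those readers. Flag single-reader changes and note that they are noisier when the reader offset is small.
2. Keep the protocol's > 0.5 progression row. Add a descriptive row, n (%) with 95% CI, for an increase above the SDC. Use 0.98 × SD for two-reader changes and 1.386 × SD for single-reader changes. Do not present it as the only valid rate.
3. In Table 14.8.2.13, show progression as n (%) with 95% CI and add the synovitis block.

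If the Week 12 dataset is already locked, label the new Week 12 rows post hoc, as CLP-004 5.1 requires.

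The cost is SAP and shell wording plus minor programming. No new reads are needed, because the SDC already requires change scores by reader. The > 0.5 count may move in either direction, so no reduction in progressors should be promised.

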8.6.2 Analysis of Exploratory Secondary Endpoints

The following endpoints will be analyzed with the CMH test, as described in Section **5.1**:

- ACR50/70 response at Week 12
- DAS28-CRP LDA/remission at Week 12
- CDAI response at Week 12
- HAQ-DI response at Week 12
- EQ-5D-5L response at Week 12
- RAMRIS bone erosion progression (> 0.5) at Week 12

The MMRM will be used to analyze the following endpoints, as described in Section **5.1**:

- Mean CDAI score change from baseline to Week 12
- Mean HAQ-DI score change from baseline to Week 12
- Mean EQ-5D-5L score change from baseline to Week 12
- Mean SF-36/PCS/MCS score change from baseline to Week 12
- Mean RAMRIS bone erosion, osteitis, synovitis, and CARLOS score change from baseline to Week 12
- Percent change in plasma biomarkers (e.g., IL-6, SAA, MMP3)

8.7 Blinding Assessment

The effectiveness of blinding of subjects, joint evaluators and Co-PI Rheumatologists will be evaluated at Week 4 and Week 12 using a blinding questionnaire with the following questions:

- I strongly believe I am [or subject is] in the treatment group and receiving therapeutic stimulation
- I somewhat believe I am [or subject is] in the treatment group and receiving therapeutic stimulation
- I somewhat believe I am [or subject is] in the control group and receiving non-therapeutic stimulation
- I strongly believe I am [or subject is] in the control group and receiving non-therapeutic stimulation
- I don't know which group I am [or subject is] and which stimulation I am [or subject is] receiving

The statistical test will be Bang's blinding index (BI) and its associated 95% confidence interval (Bang 2010). The BI will be calculated for both the ITT and PTE populations.

9 SAFETY EVALUATION

9.1 AE and SAEs

The incidence of AEs and SAEs from informed consent date to Week 12 will be tabulated. Each AE will be evaluated by clinical investigators in terms of seriousness, severity (i.e., mild, moderate, severe) and strength of relationship (i.e., not related, unlikely related, probably related, definitely related, indeterminate) to the implant procedure, implant device, stimulation, Energizer, and explant procedure. Any AE that is determined by a participating investigator to be related (definitely related or probably related) to the implant procedure, implant device, stimulation, Energizer, or explant procedure will be categorized as device related. In unblinded analyses, if the subject was assigned to the control group, but the AE indicates relationship to stimulation, the AE relationship will be updated to "not related."

For all AE tables, a subject reporting the same adverse event more than once will be counted once when calculating the number and percentage of subjects with that particular event. If a subject reports the same AE more than once or has the same AE on multiple occasions, the maximum severity grade and relationship will be presented.

The frequencies and percentages of treatment-emergent adverse events will be presented by MedDRA system organ class (SOC) and preferred term (PT). Complete subject listings of all AE will be provided. For each AE the following will be specified: start and stop dates, severity grade, MedDRA SOC and PT, relationship (not related, unlikely related, probably related, definitely related, or indeterminate) to the implant procedure, implant device, stimulation, Energizer, and explant procedure, , as well as action taken, outcome of the adverse event, and seriousness.

9.2 Protocol Deviations

All protocol deviations will be tabulated with reasons for deviations, reviewed by sponsor using blinded data and reported in compliance with the study protocol, IRB requirements and sponsor's SOPs.

Protocol deviations will be categorized as major procedural if a study subject:

- Undergoes any study-related procedure before signing an IRB-approved informed consent form, or
- Receives study treatment not consistent with the treatment assignment, or
- Is no longer eligible but received study treatment.

Summary tables with the number and percentage of subjects with protocol deviations will be provided by treatment group and by type of deviation (**Appendix B**). A by-subject listing of all protocol deviations will be provided (**Appendix C**).

A sensitivity analysis for protocol deviations that could impact the primary endpoint will be performed to address potential bias from minor deviations. Protocol deviations will be reviewed by the Sponsor and those identified as possibly impacting the primary endpoint will be summarized in the CSR.

9.3 Device Deficiencies

All device deficiencies related to the identity, quality, durability, reliability, safety or performance of the study device, including device malfunctions, use errors, and inadequate labelling will be tabulated. Summary tables with the number and percentage of device deficiencies will be provided by type (**Appendix B**). A by-subject listing of all device malfunctions will be provided (**Appendix C**).

10 STATISTICAL CONSIDERATIONS RELATED TO COVID-19

The statistical considerations detailed in this section are consistent with the FDA's guidance on the conduct of clinical trials during the COVID-19 pandemic (Guidance for Industry on Statistical Considerations for Clinical Trials During the COVID-19 Public Health Emergency; Issued June 2020) and recommendations for the statistical analysis of the primary and key secondary endpoints to help ensure that the COVID-19-related changes to the RESET-RA study conduct will provide interpretable findings with correct statistical quantification of uncertainty.

10.1 Impact of COVID-19 on Study Integrity

Unavoidable protocol modifications may be required due to COVID-19 illness and/or COVID-19 control measures to protect subject safety and the to address its impact on the ability to collect data. The context and/or reasons for post-baseline events as they relate to COVID-19, such as discontinuation of treatment, withdrawal from the trial, use of alternative or rescue treatments, missed endpoint assessments, and the use of alternative endpoint assessment methods will be

captured at the subject level. Information not specific to individual subjects, such as information on site closure (rheumatology or surgery) and its impact on disrupting administration of the investigational study device (i.e., implant procedure, device titration, device adjustments) will also be captured. This information at both the subject and site levels may be useful for incorporating into additional sensitivity analyses related to the impact of COVID-19.

